9. DIRECT ACCESS TO SOURCE DATA/DOCUMENTATION

Study visits will be conducted by an authorized D. Western Therapeutics, Inc., representative to inspect study data, subjects' medical records, and CRFs in accordance with current US Good Clinical Practices (GCP) and the respective local, national government and international regulations and guidelines.

The investigator will permit authorized representatives of D. Western Therapeutics, Inc., or its representative, the Food and Drug Administration (FDA), and any appropriate health authorities to inspect facilities and records relevant to this study.

10. DATA REVIEW AND ANALYSIS

Masked data will be continually monitored on an ongoing basis, according to the safety plan, as subjects are enrolled and complete the study. During the study, investigators, site personnel except the unmasked dosing coordinator, and D. Western Therapeutics, Inc. personnel responsible for the daily conduct of the study will remain masked to the results to maintain the scientific rigor and credibility of the trial. D. Western Therapeutics, Inc. personnel and selected external consultants will be unmasked once the data is locked. Data will then be reviewed, the safety and efficacy for each dose determined.

11. QUALITY CONTROL AND QUALITY ASSURANCE

Each investigator must adhere to the protocol as detailed in this document and agrees that any changes to the protocol must be approved by D. Western Therapeutics, Inc., prior to seeking approval from the IRB/Ethics Committee. Each investigator will be responsible for enrolling only those subjects who have met protocol eligibility criteria. During study conduct, D. Western Therapeutics, Inc. and/or its representative will conduct periodic monitoring visits to ensure that the protocol and Good Clinical Practices (GCPs) are being followed. These representatives may review source documents to confirm that the data recorded in CRFs is accurate. The investigator and institution will allow D. Western Therapeutics, Inc., representatives, or agents and appropriate regulatory authorities direct access to source documents and CRFs to perform this verification.

It is important that the investigator(s) and their relevant personnel are available during the monitoring visits and possible audits or inspections and that sufficient time is devoted to the process.

12. ETHICAL CONSIDERATIONS

This study will be conducted in accordance with current US FDA regulations, International Conference on Harmonization (ICH) guidelines, Good Clinical Practice (GCP) standards, the Declaration of Helsinki, and local ethical and legal requirements. The Principal Investigator must sign the protocol signature page to indicate acceptance of the protocol.

12.1 Informed Consent

The subject must sign the Informed Consent Document before his or her participation in the study. A copy of the Informed Consent Document must be provided to the subject or the subject's legal guardian. If applicable, it will be provided in a certified translation of the subject's first or native language. The original signed informed consent document for each participating subject shall be filed with records kept by the investigator (ISF) and must be available for verification by study monitors at any time; a copy will be given to each subject.

12.2 Institutional Review Board/Ethics Committee

This protocol, the informed consent document, relevant supporting information and all types of subject recruitment or advertisement information must be submitted to the IRB/Ethics Committee for review and must be approved before the study is initiated. Any amendments to the protocol must also be approved by the IRB/Ethics Committee prior to implementing changes in the study. The investigator is responsible for keeping the IRB/Ethics Committee apprised of the progress of the study, any SAEs, and any changes made to the protocol according to the requirements of the site's IRB.

12.3 Confidentiality

The information obtained during the conduct of this clinical study is confidential, and disclosure to third parties other than those noted below is strictly prohibited. Information obtained during the conduct of this study will be used by D. Western Therapeutics, Inc., in connection with the development of the IP. The study investigator is obliged to provide D. Western Therapeutics, Inc., or designee with complete test results and all data developed in this study. This information may be disclosed to other physicians who are participating in this trial, and to the FDA as deemed necessary by D. Western Therapeutics, Inc. Subject-specific information may be provided to other appropriate medical personnel only with the subject's permission.

12.4 Early Sponsor Discontinuation of the Trial

All clinical investigational data will be reviewed by the Medical Monitor on a regular basis. Reports of all data may be made available to the appropriate IRB/Ethics Committee and to the FDA. The clinical investigation may be suspended if the Medical Monitor, upon review and evaluation of the clinical data, finds the severity or incidence of single or total complications unacceptable for continuation of the investigation.

13. DATA HANDLING AND RECORD KEEPING

The investigator must retain all study records according to ICH guidelines and according to the record retention policies of the country where the study is being conducted. FDA requires that records be retained for at least 2 years after a marketing application is approved for the drug, or if an application is not approved, until 2 years after FDA has been notified of the discontinuation of the investigational use of the drug (21CFR312.57).

4.7	MEDICAL AND OCULAR HISTORY	
4.8	PRIOR AND CONCOMITANT MEDICATIONS	
4.9	CONCOMITANT PROCEDURES	
4.10	Treatment Exposure	
4.11	EFFICACY ANALYSES	
4.11		
4.11		
4.11		3
4.12	SAFETY ANALYSES	_
4.12		
4.12		
4.12		
4.12	1 1 2	
4.12	J = JI = G	
4.12 4.13	7.6 Dilated Ophthalmoscopy	4
4.13 4.14	SUBGROUP ANALYSIS	
	IARY OF CHANGES FROM THE PROTOCOL16	
	OF PROGRAMMING SUMMARY & ANALYSIS TABLES17	
7 APPEN	NDICES18	
7.1	APPENDIX 1 – TIME AND EVENT SCHEDULE	

Summary of Changes

Version 1.0	Initial Version
Version 2.0	Updates to reflect Protocol Version 3.0 and comments received from U.S. FDA on 4 January 2024. The Intent-to-Treat population is redefined as per FDA's comments. The main analyses are conducted on the Intent-to-Treat population instead of the Per-Protocol population. The repeated measures model of the main analysis contains additional information as per FDA's feedback. The random effect is updated to subject instead of center. Details on diurnal intraocular pressure calculations are added.

30-Jan-24

Abbreviations

AE	Adverse Event
ANCOVA	Analysis of Covariance
ATC	Anatomical Therapeutic Chemical
BCVA	Best Corrected Distance Visual Acuity
b.i.d.	twice a day
CI	Confidence Interval
IOP	Intraocular Pressure
IP	Investigational Product
ITT	Intent-to-Treat
LS	Least Square
MedDRA	Medical Dictionary for Regulatory Activities
mmHg	Millimetre of mercury
OD	right eye
OHT	Ocular Hypertension
OS	left eye
OU	both eyes
POAG	Primary Open Angle Glaucoma
PP	Per-Protocol
PT	Preferred Term
q.a.m.	every morning
q.p.m.	every afternoon/evening
RGC	retinal ganglion cells
SAP	Statistical Analysis Plan
SD	Standard Deviation
SE	Standard Error
SOC	System Organ Class
TEAE	Treatment Emergent Adverse Event
WHODRUG	World Health Organization Drug Dictionary

1 Introduction

This document presents the statistical analysis plan (SAP) for D. Western Therapeutics Institute, Inc. Protocol H1337-CS202: A Phase 2b Randomized, Double-masked, Active-controlled, Dose-response Study of the Safety and Efficacy of H-1337 in Subjects with Primary Open Angle Glaucoma (POAG) or Ocular Hypertension (OHT). This SAP describes the endpoints, datasets and analyses planned for the efficacy and safety of this study. The variables and methods described in this plan supersede those described in the protocol. If revisions are needed after finalizing, then this document will be amended. All SAP amendments will be finalized prior to locking the database. All deviations from the analyses described in the final SAP will be noted in the clinical study report.

This analysis plan is based on protocol version 3.0, dated 19JAN2024.

1.1 Study Background

Glaucoma is a slowly progressive optic neuropathy characterized by a loss of retinal ganglion cells (RGC) and optic nerve axons resulting in vision loss. As elevated intraocular pressure (IOP) is a major risk for loss of visual field and optic nerve, reduction of IOP by medical, laser and/or surgical means is the current standard of care for patients with glaucoma. While there are many therapies available, each has its own benefits and risks. Some patients, even with proper diagnosis and treatment, still continue to have progressive glaucomatous loss of visual function and/or optic nerve.

H-1337 is a selective multi-kinase inhibitor, and the proposed mechanism of action of the compound is hypothesized to involve inhibition of kinases that play a role in controlling intracellular cytoskeletal dynamics and contractility. While the regulation of IOP by the conventional (trabecular) outflow pathway is complicated, extracellular matrix expression and trabecular meshwork cytoskeletal shape and contractility appear to be important to control outflow resistance.

In a previous controlled study, H-1337 Ophthalmic Solution showed clinically and statistically significant ocular hypotensive activity and was well tolerated, with a relatively low incidence of hyperemia. The present study aims to extend the previous findings with additional concentrations and doses, as well as including an active control (timolol ophthalmic solution).

2 Study Objectives

2.1 Primary Objective

The primary objective of this study is to evaluate the ocular hypotensive efficacy of 3 dose regimens of H-1337 compared to timolol maleate 0.5% in subjects with POAG or OHT treated for up to 28 days.

2.2 Secondary Objective

The secondary objective of this study is to evaluate the local ocular and systemic safety of 3 dose regimens of H-1337.

2.3 Exploratory Objective

The exploratory objective of this study is to evaluate the efficacy of diurnal IOP measurements of 3 dose regimens of H-1337 compared to timolol 0.5%.

2.4 Primary Efficacy Endpoint

The primary efficacy measure is the mean change in IOP from Baseline IOP (mmHg) in the study eye for each group on Day 28 at each matched time point as compared to Timolol.

2.5 Secondary Efficacy Endpoints

The secondary efficacy endpoints of the study are as follows:

- The observed IOP, change from Baseline, and % change from Baseline in IOP in the study eye at each matched time point at each visit.
- The observed mean diurnal IOP, change from Baseline and % change from Baseline in the study eye in mean diurnal IOP at each visit,
- The proportion of subjects with IOP \leq 18 mmHg in their study eye at each time point at each visit, and with the mean diurnal IOP \leq 18 mmHg in the study eye for each visit.

2.6 Safety Endpoints

The safety endpoints of the study are as follows:

- Incidence of Ocular and systemic Adverse Events (AE),
- The observed blood pressure and pulse, and change from Baseline at each visit,
- The observed best-corrected visual acuity (BCVA) and change from Baseline at each visit.

3 Study Design and Procedures

3.1 Overall Study Design

This is a parallel group, double-masked, active-controlled study to evaluate the ocular hypotensive efficacy of 3 dose regimens of H-1337 compared to timolol maleate 0.5% in subjects with POAG or OHT treated for up to 28 days.

Each subject's participation will consist of two phases: a Screening Phase (Screening and Baseline Visits) where subjects will suspend dosing of any current ocular hypotensive therapy, and a Dosing Phase, starting on Day 1.

Following the washout period (if required), the subject will return for applicable inclusion/exclusion evaluations at the Baseline Visit (Day 1). A subject meeting all inclusion/exclusion criteria at Pre-T₀ will be randomized to the Investigational Product (IP). Both eyes will be dosed and evaluated for safety throughout the trial.

Dosing will be initiated at Day 1. Subjects will be dosed for up to 28 days during which time they will be monitored for safety, tolerability, and efficacy.

Subjects will be randomized to 4 arms:

- Group 1: H-1337 0.6% Ophthalmic Solution b.i.d.
- Group 2: H-1337 1.0% Ophthalmic Solution b.i.d.
- Group 3: H-1337 1.0% Ophthalmic Solution q.a.m. and H-1337 placebo q.p.m.
- Group 4: Timolol 0.5% Ophthalmic Solution b.i.d

The trial will evaluate the safety and efficacy of 3 dose regimens of H-1337 and timolol maleate (0.5%, b.i.d.) OU for 28 days.

Efficacy evaluation will be made based upon the study eye.

3.2 Schedule of Visits and Assessments

The schedule of visits is defined as follow:

- Screening Visit
- Day 0
- Day 1
- Day 7
- Day 14
- Day 28

A schedule of study assessments and procedures is available in Appendix 1.

3.3 Sample Size Justification

The sample size is driven by interest in the IOP lowering effect of H-1337. The study is designed to test whether one or more concentrations of H-1337 are non-inferior to the timolol control in the reduction of IOP. As benefit is represented by a negative number, non-inferiority is achieved when the upper limit of the confidence interval of the difference in treatment (H-1337 minus Timolol) is strictly lower than the non-inferiority margin.

A sample size of 45 subjects per group will allow for at least 90% power to establish non-inferiority of H-1337 over Timolol based on a non-inferiority limit of 2 mmHg, a standard deviation of 3.0 mmHg and a 1-sided t-test (alpha=0.05).

Assuming that 10% of the subjects will not be eligible in the Intent-to-Treat (ITT) population, a total of 50 subjects per group is required.

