Administration: Study Design:	The trial will evaluate the safety and efficacy of 3 dose regimens of H-1337 (0.6% b.i.d., 1.0% b.i.d. and 1.0% q.a.m., and timolol maleate (0.5%, b.i.d.) OU for 28 days. Efficacy assessments will be made based upon the study eye. The study eye is the eye that meets all entry criteria including the intraocular pressure (IOP) inclusion criteria. If both eyes qualify the study eye is the eye with the higher 8 am IOP on Baseline (Day 1). If both eyes have the same 8 am IOP on Baseline (Day 1), the study eye is the right eye.
Primary Efficacy Measure:	Change from baseline in IOP in 3 dose regimens of H-1337 compared to timolol 0.5%., b.i.d. at 28 days in subjects with POAG or ocular hypertension.

Secondary Efficacy Measure:	 Mean IOP in 3 dose regimens of H-1337 compared to timolol 0.5%., b.i.d. at 28 days in subjects with POAG or ocular hypertension. Mean diurnal IOP in 3 dose regimens of H-1337 compared to timolol 0.5%., b.i.d. at 28 days in subjects with POAG or ocular hypertension. Proportion of subjects with IOP ≤ 18 mmHg at each time point at each visit, and with the mean diurnal IOP ≤ 18 mmHg for each visit.
Safety Endpoints:	Ocular and systemic Adverse Events (AE)
Study Assessments:	The following assessments and procedures will be performed: • Medical and ocular history • Prior and current concomitant medications and procedures • Adverse events • Heart rate and blood pressure • Best-corrected visual acuity (ETDRS) OU • Biomicroscopy OU • Conjunctival Hyperemia Grading OU • Intraocular pressure (Goldmann tonometry) OU • Gonioscopy OU • Pachymetry OU • Visual field testing (automated, threshold) OU • Ophthalmoscopy (dilated) OU
Statistical Considerations:	This trial has \geq 90% power to detect a clinically significant difference of 2.0 mm Hg, assuming SD of 3.0 mm Hg (ALY337-201), and α =0.05 (1-sided). A hierarchical analysis will be performed starting with 1.0% H-1337 b.i.d. Thus, no adjustment for multiplicity will be performed.
Pharmacokinetic Endpoints	None

Inclusion Criteria:

To be eligible for trial participation subjects must meet all the following criteria:

- 1. 18 years of age or older.
- 2. Diagnosis of bilateral primary open angle glaucoma or ocular hypertension.
- 3. One qualifying IOP criteria after washout:
 - Baseline (Day 1) at T_0 ($T_0 = 8$ am ± 30 min [IOP time]) IOP ≥ 23 mmHg in the study eye.
- 4. IOP criteria after washout ≤ 32 mmHg OU at all qualifying time points/visits.

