8. STATISTICAL PLAN

8.1 Sample Size

The sample size is driven by interest in the IOP lowering effect of H-1337. The study is designed to test whether one or more concentrations of H-1337 are non-inferior to the timolol control in the reduction of IOP. As benefit is represented by a negative number, non-inferiority

is achieved when the upper limit of the confidence interval of the difference in treatment (H-1337 minus Timolol) is strictly lower than the non-inferiority margin.

A sample size of 45 subjects per group will allow for at least 90% power to establish non-inferiority of H-1337 over Timolol based on a non-inferiority limit of -2 mmHg, a standard deviation of 3.0 mmHg and a 1-sided t-test (alpha=0.05).

Assuming that 10% of the subjects will not be eligible in the ITT population, a total of 50 subjects per group is required.

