8.4 Significance and Adjustment for Multiple Comparisons

Change from Baseline in IOP (mmHg) at Day 28 and Day 1 (on-treatment time points) in the study eye is the primary efficacy endpoint. It will be summarized by timepoint and treatment group in the ITT population primarily and in the PP population secondarily. The differences between treatments (H-1337 vs Timolol) will be calculated for each H-1337 treatment group. A timematched longitudinal model adjusting for baseline and including a random effect for subject will be used to calculate the LSmean, SE, and 2-sided 95% CI for the between treatments differences. To account for the multiple comparisons of the primary endpoints, adjustment for multiplicity will be fulfilled by using a hierarchical testing, based on a fixed-sequence procedure defined in

Table 3. First, the primary endpoint is tested for non-inferiority at all 4 time points at Day 28 (excluding +12 hours) and all 3 on-treatment time points at Day 1 (excluding +12 hours) for the first pre-defined Group comparison listed in Table 3. If the upper limit of the 2-sided 95% CI of the difference between H-1337 and Timolol is strictly lower than the value 1.5, then non-inferiority is concluded. If non-inferiority is concluded at the 7 timepoints, then testing of the second listed Group Comparison in Table 3 can take place at the 2-sided alpha level of 0.05. Otherwise, non-inferiority cannot be concluded and no further formal testing takes place. The same sequential approach is then applied to the remaining endpoints listed in Table 3.

Table 3 Pre-defined Sequence for Hierarchical Testing

Order	Group Comparison	Non-Inferiority Criteria
1	H-1337 1.0% Ophthalmic Solution b.i.d. vs	1.5 threshold at all 7 time points
	Timolol 0.5% Ophthalmic Solution b.i.d	
2	H-1337 0.6% Ophthalmic Solution b.i.d vs	1.5 threshold at all 7 time points
	Timolol 0.5% Ophthalmic Solution b.i.d	
3	H-1337 1.0% Ophthalmic Solution q.a.m. vs	1.5 threshold at all 7 time points
	Timolol 0.5% Ophthalmic Solution b.i.d	
4	H-1337 1.0% Ophthalmic Solution b.i.d. vs	1.0 threshold at 5 or more time points
	Timolol 0.5% Ophthalmic Solution b.i.d	
5	H-1337 0.6% Ophthalmic Solution b.i.d vs	1.0 threshold at 5 or more time points
	Timolol 0.5% Ophthalmic Solution b.i.d	
6	H-1337 1.0% Ophthalmic Solution q.a.m. vs	1.0 threshold at 5 or more time points
	Timolol 0.5% Ophthalmic Solution b.i.d	

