4.3 Adjustment for Multiplicity

To account for the multiple comparisons of the primary endpoints, adjustment for multiplicity will be fulfilled by using a hierarchical testing, based on a fixed-sequence procedure defined in Table 1.

First, the primary endpoint is tested for non-inferiority at all 5 time points at Day 28 and all 4 ontreatment time points at Day 1 for the first pre-defined Group comparison listed in Table 1. If the upper limit of the 2-sided 95% CI of the difference between H-1337 and Timolol is strictly lower than the value 1.5, then non-inferiority is concluded. If non-inferiority is concluded at the 9 timepoints, then testing of the second listed Group Comparison in Table 1 can take place at the 2-sided alpha level of 0.05. Otherwise, non-inferiority cannot be concluded and no further formal testing takes place.

The same sequential approach is then applied to the remaining endpoints listed in Table 1. Endpoints are tested in the order defined in Table 1.

For the first 3 rows in Table 1, non-inferiority at the 1.5 threshold at all 9 timepoints must be shown to allow to proceed to the next row. For the last 3 rows in Table 1, non-inferiority at the 1.0 threshold at 5 or more timepoints must be shown to allow to proceed to the next row.

Table 1 Pre-defined Sequence for Hierarchical Testing

Order	Group Comparison	Non-Inferiority Criteria
1	H-1337 1.0% Ophthalmic Solution b.i.d. vs	1.5 threshold at all 9 time points
	Timolol 0.5% Ophthalmic Solution b.i.d	
2	H-1337 0.6% Ophthalmic Solution b.i.d vs	1.5 threshold at all 9 time points
	Timolol 0.5% Ophthalmic Solution b.i.d	
3	H-1337 1.0% Ophthalmic Solution q.a.m. vs	1.5 threshold at all 9 time points
	Timolol 0.5% Ophthalmic Solution b.i.d	
4	H-1337 1.0% Ophthalmic Solution b.i.d. vs	1.0 threshold at 5 or more time points
	Timolol 0.5% Ophthalmic Solution b.i.d	
5	H-1337 0.6% Ophthalmic Solution b.i.d vs	1.0 threshold at 5 or more time points
	Timolol 0.5% Ophthalmic Solution b.i.d	
6	H-1337 1.0% Ophthalmic Solution q.a.m. vs	1.0 threshold at 5 or more time points
	Timolol 0.5% Ophthalmic Solution b.i.d	

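### The stated power of at least 90% belongs to a more lenient test (margin 2 mmHg, one-sided 0.05) than the one that decides the trial (margin 1.5 mmHg, 2-sided 95% CI, every time point)

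*SAP*

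**What the plan says.** **Sizing basis.** SAP 3.3 says that 45 subjects per arm "will allow for at least 90% power to establish non-inferiority of H-1337 over Timolol based on a non-inferiority limit of 2 mmHg". It assumes an SD of 3.0 mmHg and a one-sided t-test at 0.05, and raises 45 to 50 for a 10% loss. Protocol 8.1 has the same text with the limit printed as -2. The protocol synopsis gives the same power, SD and alpha for detecting a 2.0 mmHg difference and names no margin.

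**Decision rule.** SAP 4.3 concludes non-inferiority on this condition: "If the upper limit of the 2-sided 95% CI of the difference between H-1337 and Timolol is strictly lower than the value 1.5". For the first three rows of SAP Table 1, "non-inferiority at the 1.5 threshold at all 9 timepoints must be shown to allow to proceed to the next row". If a row fails: "Otherwise, non-inferiority cannot be concluded and no further formal testing takes place". Protocol 8.4 has the same margin and interval but counts fewer points: "If non-inferiority is concluded at the 7 timepoints, then testing of the second listed Group Comparison in Table 3 can take place". On precedence, SAP 1 says: "The variables and methods described in this plan supersede those described in the protocol".

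**Model.** SAP 4.11.1 takes the differences from a longitudinal model adjusted for baseline. It tests treatment by visit and treatment by time point, and uses a main-effect model if no interaction is detected.

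**Disclosure.** SAP 5 notes that the protocol was sized on a limit of 2 while 1.5 and 1 are used in the analysis, and that Day 1 points have been added. It attributes the limit of 2 to the protocol, although SAP 3.3 repeats it. It does not mention alpha and gives no new power.

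**The concern.** The sizing calculation and the decision rule differ in three respects, and each makes the rule harder to meet. The margin falls from 2 to 1.5 mmHg. The one-sided error rate falls from 0.05 to 0.025, because the rule uses the upper limit of a 2-sided 95% interval. One comparison becomes 9 (SAP) or 7 (protocol) that must all succeed. The only power figure in either document therefore does not describe the test that decides the trial.

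What is at stake is interpretation. The first row, 1.0% b.i.d. against timolol, gates every later comparison. A reader who trusts 90% would take a failed first row as strong evidence against H-1337. Under the planned rule, an equally effective drug could fail quite often.

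**Working it through.** **Inputs from the documents:** n = 45 (sizing) and 50 (randomised) per arm; SD 3.0; margin 2 with one-sided 0.05 (SAP 3.3); margin 1.5 with one-sided 0.025, and 9 or 7 points (SAP 4.3, protocol 8.4). **Assumed:** true difference 0, which the stated 90% also needs, and for the all-points figures an equal within-subject correlation ρ of 0.5–0.8.

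**1. One time point.** SE = SD × √(2/n). Power is the probability that a noncentral t variable with 2n − 2 df and noncentrality margin/SE exceeds the critical t. At n = 45, SE = 3 × √(2/45) = 0.632; at n = 50, SE = 0.600.

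- Plan's own figure, n = 45: noncentrality 2/0.632 = 3.16, critical t 1.662, power 93.2%. The plan's statement reproduces.
- Planned rule, n = 45: noncentrality 1.5/0.632 = 2.37, critical t 1.987, power 65.0%.

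| Test at one point, SD 3.0 | n = 45 | n = 50 |
|---|---|---|
| Margin 2, one-sided 0.05 (as stated) | 93.2% | 95.2% |
| Margin 2, one-sided 0.025 (alpha change only) | 87.9% | 91.0% |
| Margin 1.5, one-sided 0.05 (margin change only) | 76.1% | 79.9% |
| Margin 1.5, one-sided 0.025 (as planned) | 65.0% | 69.7% |

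If baseline adjustment brought the residual SD to 2.5, the last row would be 80.4% / 84.4%. Reaching 90% at one point needs an SD of about 2.17 (n = 45) or 2.29 (n = 50).

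**2. All points, differences estimated separately.** This is the probability that all k upper limits fall below 1.5, with equicorrelated estimates, by numerical integration and confirmed by simulation.

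**3. All points, main-effect model.** One common difference decides every point. The formula of step 1 applies, with the SD of a subject's mean over k points: SD × √((1 + (k − 1)ρ)/k). For k = 9 and ρ = 0.5 this is 3 × √(5/9) = 2.24; for ρ = 0.8 it is 3 × √(7.4/9) = 2.72.

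| SD 3.0, ρ = 0.5 to 0.8 | n = 45 | n = 50 |
|---|---|---|
| Separate estimates, 9 points | 21.0–38.3% | 25.9–43.7% |
| Separate estimates, 7 points | 24.8–40.8% | 30.1–46.3% |
| Main-effect model, 9 points | 88.2–73.5% | 91.3–77.9% |
| Main-effect model, 7 points | 87.3–73.1% | 90.6–77.6% |

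A higher correlation helps the separate estimates and hurts the common difference. With SD 2.5, separate estimates over 9 points give about 41–65% and the main-effect model 87–98%.

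**4. Choosing between the two.** SAP 4.11.1 lets an interaction test decide but gives no level. I simulated four arms with one joint treatment-by-time test at an assumed 0.05. With no true interaction, the main-effect branch is used in about 95% of runs, and overall power is about 71–84% (n = 45) or 76–88% (n = 50). If the true difference runs linearly from -0.5 to +0.5 mmHg over the points (mean 0, n = 50), that branch is used in 32–75% of runs and power is about 43–71%. From -1 to +1 the figures are 0–11% and 10–15%. These patterns are illustrations only.

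The 9-point figures assume full n at +12 h. That measurement is optional for new subjects under protocol version 3.0, so 9-point power with separate estimates would be lower still.

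**The case against.** Nothing is miscalculated: the 90% is correct for the inputs given. SAP 5 admits the margin change, and the decision rule is stated openly. That is true, but it leaves the planned rule without a power figure and the alpha change unmentioned.

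The all-points ranges rest on a correlation that the documents do not give, and they are not bounds. At ρ = 0.3 and SD 3.0 the main-effect model gives 96–98% and separate estimates 12–21%; at ρ = 0.9 they give 69–74% and 47–54%. This stands. The shortfall is not certain under the main-effect model, and at ρ of 0.4 or lower even n = 45 exceeds 90% there.

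The documents do not say whether SD 3.0 is a raw, change or residual SD, and baseline adjustment could lower it. This also stands, although at 2.5 one-point power is still only 80–84%. Nor need the true difference be 0: if H-1337 were better than timolol by 0.5 mmHg, one-point power would be 87.9% / 91.0%. The stated 90% rests on no such advantage, so the like-for-like comparison is at 0.

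Finally, no estimate or interval depends on the power sentence, and the intervals will be reported whatever happens. That limits the weight of the point but does not remove it.

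**Conclusion.** The concern holds. The power statement is right for its own inputs but is not a property of the test that decides the trial. On the documents' n and SD with a true difference of 0, one-point power is 65–70%, and this needs no correlation assumption. Over all points at ρ = 0.5–0.8, it is about 21–46% with separate estimates and 73–91% with one common difference. Within that range and at SD 3.0, 90% is reached only under the main-effect model, with n = 50 and a correlation of about 0.5. This should be fixed. The consequence is confined to how a failed first row is read.

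**What to change.** In SAP 3.3, keep the present calculation, label it as the original sizing basis, and add wording such as:

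> The criterion in Section 4.3 is stricter: the upper limit of the 2-sided 95% CI must be below 1.5 mmHg at all 9 time points. With 45 to 50 per group, SD 3.0 and true difference 0, power is 65–70% at one time point. For all 9, assuming correlation 0.5–0.8, it is about 21–44% if differences are estimated by time point and 73–91% if the main-effect model supplies one common difference. With residual SD 2.5 these are 80–84%, 41–65% and 87–98%.

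Give the 7-point figures as well (25–46% and 73–91% at SD 3.0) until the two documents agree. State whether SD 3.0 is raw, change or residual. In SAP 5, add the move from one-sided 0.05 to a 2-sided 95% CI. Two small wording points: print 2 rather than -2 in protocol 8.1, and describe the 10% allowance as missing IOP data, since SAP 3.4.2 puts every randomised subject in the ITT population.

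**Cost.** One paragraph and one line, by a SAP amendment before database lock (SAP 1). Protocol 8.1 and the synopsis can follow at the next amendment, which needs IRB approval (protocol 12.2). No estimate, interval, decision rule or enrolment changes; the price is a less favourable stated power.

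Two related matters should be handled separately because they do touch the decision rule: reconciling 7 with 9 time points, and stating how the all-points requirement works under the main-effect model.
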